3.2 Dexamethasone (Decadron) (NSC-34521)

a. DESCRIPTION

Dexamethasone (Decadron) is a synthetic adrenocortical steroid and is readily absorbed from the gastrointestinal tract. Chemically, dexamethasone is 9-fluoro-11b, 17, 21-trihydroxy-16a-methyl-pregna-1, 4-diene-3, 20-dione.

b. TOXICOLOGY

Human Toxicology: Possible adverse effects associated with the use of dexamethasone are: fluid and electrolyte disturbances, congestive heart failure in susceptible persons, hypertension, euphoria, personality changes, insomnia, exacerbation of infection (e.g., tuberculosis), exacerbation or symptoms of diabetes, psychosis, muscle weakness, osteoporosis, vertebral compression fractures, pancreatitis, esophagitis, peptic ulcer, dermatologic disturbances, convulsions, vertigo and headache, endocrine abnormalities, ophthalmic changes, and metabolic changes. Some patients have experienced itching and other allergic, anaphylactic or other hypersensitivity reactions. Withdrawal from prolonged therapy may result in symptoms including fever, myalgia and arthralgia. Phenytoin phenobarbital and ephedrine enhance metabolic clearance of corticosteroids.

Corticosteroids should be used cautiously in patients with hypothyroidism, cirrhosis, ocular herpes simplex, existing emotional instability or psychotic tendencies, nonspecific ulcerative colitis, diverticulitis, fresh intestinal anastomoses, peptic ulcer, renal insufficiency, hypertension, osteoporosis and myasthenia gravis. Immunization procedures (especially smallpox vaccination) should not be undertaken in patients on corticosteroids.

c. PHARMACOLOGY

Kinetics: Natural and synthetic glucocorticoids are readily and completely absorbed from the GI tract. Dexamethasone is insoluble in water. Glucocorticoids have salt-retaining properties, although dexamethasone nearly completely lacks this property. Dexamethasone may suppress the body's response to viral and bacterial infections.

Formulation: Dexamethasone is available for injection as follows: EQ 10 mg phosphate/mL, EQ 24 mg phosphate/mL and EQ 4 mg phosphate/mL.

Storage and Stability: Dexamethasone is to be stored at room temperature.

Administration: For this study, the drug is administered by IV.

Supplier: Dexamethasone is commercially available and therefore is to be purchased by a third party. This drug will not be supplied by the NCI.

Please refer to the Physician Desk Reference and package insert for complete information.

4.0 STAGING CRITERIA

4.1 Diagnostic Criteria

Multiple Myeloma – normally all three are required, except for circumstances outlined in notes a-c.

Monoclonal plasma cells in the bone marrow $\geq 10\%$ and/or presence of a biopsy-proven plasmacytoma.^a

Monoclonal protein present in the serum and/or urine^b

Myeloma-related organ dysfunction (1 or more from the CRAB list below)^c

- [C] Calcium elevation in the blood (serum calcium > 10.5 mg/L or upper limit of normal)
- [R] Renal insufficiency (serum creatinine > 2 mg/dl)
- [A] Anemia (hemoglobin < 10 g/dl or 2 g $<$ normal)
- [B] Lytic bone lesions or osteoporosis^a

^a If a solitary (biopsy-proven) plasmacytoma or osteoporosis alone (without fractures) are the sole defining criteria, then $\geq 30\%$ plasma cells are required in the bone marrow.

^b If no monoclonal protein is detected (non-secretory disease), then $\geq 30\%$ monoclonal bone marrow plasma cells and/or a biopsy-proven plasmacytoma required.

^c A variety of other types of end organ dysfunctions can occasionally occur and lead to a need for therapy. Such dysfunction is sufficient to support classification as myeloma if proven to be myeloma related.

Diagnostic criteria are based on International Myeloma Foundation guidelines (<http://myeloma.org/main.jsp?type=article&id=1045>).

NOTE: Patients with light chain myeloma are eligible; however, patients with non-secretory disease are not eligible for this study. There are no exceptions to this based on diagnostic criteria in footnote "b" above.

4.2 International Staging System

New International Staging System		
Stage	Criteria	Median Survival (months)
I	Serum β 2-microglobulin < 3.5 mg/L Serum albumin \geq 3.5 g/dL	62
II	Not Stage I or III	44
III	Serum β 2-microglobulin > 5.5 mg/L	29

There are 2 categories for Stage II: serum β 2-microglobulin < 3.5 mg/L but serum albumin < 3.5 g/dL; or serum 3.5 to <5.5 mg/L irrespective of the serum albumin level.

5.0 ELIGIBILITY CRITERIA

Each of the criteria in the following section must be met in order for a patient to be considered eligible for registration. Use the spaces provided to confirm a patient's eligibility. For each criterion requiring test results and dates, please record this information on the Onstudy Form and submit via Medidata Rave® (see Section [14.0](#)). Any potential eligibility issues should be addressed to the Data Operations Center in Seattle at [name] prior to registration.

In calculating days of tests and measurements, the day a test or measurement is done is considered Day 0. Therefore, if a test is done on a Monday, the Monday 4 weeks later would be considered Day 28. This allows for efficient patient scheduling without exceeding the guidelines. **If Day 7, 14 or 28 falls on a weekend or holiday, the limit may be extended to the next working day.**

SWOG Patient No. _____

Patient's Initials (L, F, M) _____

5.1 Registration Step 1: Initial Randomization

- _____ a. Patients must have a confirmed diagnosis of symptomatic multiple myeloma and must be currently relapsed or refractory. Except where otherwise indicated below that assessment is required within 14 days, all tests for establishing disease status must be completed within 28 days prior to registration and documented on the Baseline Tumor Assessment Form for Multiple Myeloma.
- _____ b. Patients must have measurable disease as defined in Section [10.1a](#) within 28 days prior to registration. Patients must have SPEP and UPEP within 14 days prior to registration.
- _____ c. Patients must have received at least one prior regimen of chemotherapy for symptomatic multiple myeloma. Patients may not have more than six (6) previous regimens of therapy for the disease. Prior chemotherapy must have been completed at least 21 days prior to registration.

For study purposes, a regimen is defined as follows:

- An anti-myeloma therapy used at the time of initial diagnosis or documented disease progression which is given with the intent to decrease disease burden.
- Any Maintenance therapy used after an Induction should be considered part of that Induction regimen.
- Use of any agent or combination of agents more than once during the patient's disease history for separate documented disease progressions will be counted as separate regimens (e.g., if a patient receives lenalidomide/bortezomib at initial diagnosis and achieves response, but then progresses and receives lenalidomide/bortezomib after progression, these count as 2 separate regimens.)
- In cases of allogeneic or autologous stem cell transplant, the entire Induction + stem cell mobilization + Conditioning + planned Maintenance should be considered one regimen.

- _____ d. Patients may not have received any prior carfilzomib treatment.
- _____ e. Patients must not be receiving any other concurrent therapy considered to be investigational. Patients must not be planning to receive any radiotherapy (except localized radiation for palliative care). Patients must not be planning to receive any concurrent chemotherapy, immunotherapy, radiotherapy or other treatment with curative intent.

SWOG Patient No. _____

Patient's Initials (L, F, M) _____

_____ f. Patients must have complete history and physical examination within 28 days prior to registration.

_____ g. Patients must have baseline PET scan within 28 days prior to registration. In the event that a patient had a standard of care PET scan prior to providing informed consent, the scan need not be repeated provided that it occurred within the 28 day window. Note that images are submitted centrally for review as outlined in Section [15.1](#).

_____ h. Patients with non-secretory MM or known primary amyloidosis are not eligible.

_____ i. Patients must be ≥ 18 years of age.

_____ j. Patients must have Zubrod Performance Status 0-2 (see Section [10.6](#)).

_____ k. Patients must not have clinically significant illness including uncontrolled, active infection requiring intravenous antibiotics, New York Heart Association (NYHA) Class III or Class IV heart failure (see Appendix [18.3](#)), unstable angina pectoris, myocardial infarction within the past 6 months, or \geq Grade 3 cardiac arrhythmias.

_____ l. Patients must have undergone an EKG within 28 days prior to registration.

_____ m. Patients must have an ECHO with ejection fraction $\geq 45\%$ within 28 days prior to registration. .

_____ n. Patients must not have $>$ Grade 2 neuropathy and/or POEMS syndrome (plasma cell dyscrasia with polyneuropathy, organomegaly, endocrinopathy, monoclonal protein, and skin changes).

_____ o. Patients must have adequate liver function as evidenced by total bilirubin $\leq 1.5 \times$ upper limit of normal (ULN) and SGOT **and** SGPT $\leq 3 \times$ ULN within 14 days prior to registration.

_____ p. Patients must have adequate bone marrow function as defined by the following within 14 days prior to registration: ANC $\geq 1,000$ cell/mm 3 without growth factor support, AND platelets $\geq 50,000$ cells/mm 3 for patients who have bone marrow plasmacytosis $< 50\%$ or $\geq 30,000$ cells/mm 3 for patients who have bone marrow plasmacytosis of $\geq 50\%$.

_____ q. Patients must have calculated or measured creatinine clearance ≥ 30 ml/min within 14 days prior to registration.

CrCl =
$$\frac{(140 - \text{patient's age} \times \text{patient's weight in kilograms}^*) \times 0.85 \text{ (if female)}}{72 \times \text{patient's serum creatinine}^{**}}$$

* The kilogram weight is the patient weight with an upper limit of 140% of the IBW.

** Actual lab serum creatinine value with a minimum of 0.8 mg/dl.

_____ r. Patients who are known to be HIV+ are eligible providing they meet all of the following additional criteria within 28 days prior to registration:

- CD4 cells $\geq 500/\text{mm}^3$
- Viral load of < 50 copies HIV mRNA/mm 3 if on cART or $< 25,000$ copies HIV mRNA if not on cART
- No zidovudine or stavudine as part of cART

Patients who are HIV+ and do not meet all of these criteria are not eligible for this study.

SWOG Patient No. _____

Patient's Initials (L, F, M) _____

s. Patients with known Hepatitis B or Hepatitis C infection must have viral load < 800,000 IU/L within 28 days prior to registration.

t. Patients must have baseline skeletal survey to document lytic lesions, osteopenia or compression fracture within 28 days prior to registration.

u. Patients may have received palliative XRT for local disease control with no curative intent. XRT must be completed at least 7 days prior to registration.

v. Patients must be offered participation in specimen submission for translational medicine studies and banking. With patient consent, specimens must be submitted as outlined in Section [15.2](#).

w. Patients must not be pregnant or nursing due to the teratogenic nature of the study drugs. Women/men of reproductive potential must have agreed to use an effective contraceptive method. A woman is considered to be of "reproductive potential" if she has had menses at any time in the preceding 12 consecutive months. In addition to routine contraceptive methods, "effective contraception" also includes heterosexual celibacy and surgery intended to prevent pregnancy (or with a side-effect of pregnancy prevention) defined as a hysterectomy, bilateral oophorectomy or bilateral tubal ligation. However, if at any point a previously celibate patient chooses to become heterosexually active during the time period for use of contraceptive measures outlined in the protocol, he/she is responsible for beginning contraceptive measures.

x. No other prior malignancy is allowed except for the following: adequately treated basal cell or squamous cell skin cancer, in situ cervical cancer or any other cancer in situ, adequately treated Stage I or II cancer from which the patient is currently in complete remission, or any other cancer from which the patient has been disease free for three years.

y. Patients or their legally authorized representative must be informed of the investigational nature of this study and must sign and give written informed consent in accordance with institutional and federal guidelines.

z. As a part of the OPEN registration process (see Section [13.2](#) for OPEN access instructions) the treating institution's identity is provided in order to ensure that the current (within 365 days) date of institutional review board approval for this study has been entered in the system.

SWOG Patient No. _____

Patient's Initials (L, F, M) _____

5.2 Registration Step 2: Crossover

- a. Patient must have been eligible for and initially randomized to Arm 1 (low dose carfilzomib), begun Cycle 2 of treatment, and progressed prior to completing 12 cycles of protocol therapy.
- b. At least 14 days and no more than 28 days must have elapsed between the last day of treatment on Arm 1 and registration to Arm 3.
- c. Patients must have recovered from all non-hematologic toxicities to \leq Grade 2 and from all hematologic toxicities to \leq Grade 3 prior to registration.
- d. Patients must have begun Cycle 2 (carfilzomib - 27 mg/m²) and must not have received any dose reduction for toxicity in the last cycle of treatment, immediately preceding progression.
- e. Patients must have SPEP and kappa and lambda light chain testing performed within 14 days prior to registration in order to establish baseline measurements.
- f. Patients must not have ejection fraction decrease $> 10\%$ from baseline (as determined by ECHO), or other ejection fraction decrease accompanied by other clinical signs/symptoms of NYHA Class III or IV heart failure, measured within 28 days prior to registration. If any question exists regarding individual patient eligibility in this situation, contact the Study Chair for determination.

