7.1 General Considerations

- a. Patients must have creatine kinase (CK), cardiac-specific troponin T (TnT) and/or troponin I (TnI) testing—both TnT and TnI preferred if available, creatine kinase-MB (CK-MB), brain natriuretic peptide (BNP) and/or proBNP performed on Cycle 1, Day 1. See [Section 9.0](#) for additional timepoints. In the event that Cycle 1, Day 1 laboratory tests are resulted and the patient no longer meets one or more of the eligibility criteria, treatment must be held. Laboratory tests and any associated supportive care must be repeated. If the repeat lab results fall within the eligibility criteria, treatment may be resumed. In the event that treatment must be held for \geq 28 days, the patient must be removed from the protocol.
- b. Patients on Arm 1 will receive dexamethasone/low-dose carfilzomib for up to 12 cycles or until progression that occurs after the start of Cycle 2, whichever comes first. If patient progresses after the start of Cycle 2 and prior to completion of 12 cycles, the patient will cross-over and be registered to Arm 3 where they may receive up to an additional 12 cycles of treatment.
- c. Results of Day 1 laboratory tests are not required prior to starting treatment for each cycle subsequent Cycle 1 (see Section 7.1a for instructions regarding D1, C1 results). If lab results are abnormal or indicative of adverse events, the treating physician should refer to Section 8.0 for dose modifications, and Response Assessments should be conducted at time of dose modification and as indicated in [Section 9.0](#). If dose modification is not indicated, the physician should otherwise continue treatment at physician discretion.
- d. Patients on Arm 2 will receive dexamethasone/high dose carfilzomib for up to 12 cycles, or until progression that occurs after the start of Cycle 2, whichever comes first. If a patient progresses after the start of Cycle 2, the patient will discontinue protocol treatment.

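### Crossover criterion 5.2f limits ejection fraction only by change from baseline, so it can admit a patient below the 45% Step 1 floor to 56 mg/m²

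*Combined protocol and SAP*

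**What the plan says.** **Step 1.** Section 5.1m states "Patients must have an ECHO with ejection fraction" of at least 45% within 28 days before registration. Section 5.1k also excludes, among other conditions, "unstable angina pectoris, myocardial infarction within the past 6 months".

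**Step 2.** Section 5.2 has its own list, items a to f.

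- 5.2a: "Patient must have been eligible for and initially randomized to Arm 1", which refers to eligibility at the time of randomization.
- 5.2c: "Patients must have recovered from all non-hematologic toxicities to" Grade 2 or lower.
- 5.2d: the patient "must not have received any dose reduction for toxicity in the last cycle of treatment, immediately preceding progression".
- 5.2f: "Patients must not have ejection fraction decrease" of more than 10% from baseline by ECHO, nor any other decrease accompanied by signs or symptoms of NYHA Class III or IV heart failure, measured within 28 days before Step 2 registration. It adds: "If any question exists regarding individual patient eligibility in this situation, contact the Study Chair for determination".

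**Dose.** On Arms 1 and 2, Cycle 1 is given at 20 mg/m² (7.3a). Arm 3 starts at 56 mg/m² in Cycle 1 (7.4, footnote a).

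**The concern.** Both limbs of 5.2f are changes from baseline, with no lower limit beneath them. At Step 1 a patient with EF of 44% may not receive a first dose of 20 mg/m². At Step 2 a patient whose EF has gone from 46% to 44% satisfies 5.2f on either reading of 10% and may start at 56 mg/m². The two entry rules therefore disagree for patients with low baseline EF. Unstable angina and recent infarction, both Step 1 exclusions, are likewise not named in 5.2.

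What is at stake is the safety of a few patients at crossover. Crossover follows first progression, so the randomized PFS comparison does not depend on it.

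**Working it through.** The plan states no figure on this point, so there is none to reproduce. The check covers the text, the arithmetic of 5.2f, and the likely number of patients.

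**1. Does other text supply an EF floor at Step 2?**

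- 5.2a looks back to Step 1 eligibility. Section 5.1 cannot carry over whole, because 5.1d bars prior carfilzomib. The general rule in 13.5a therefore does not import 5.1m.
- 7.1a re-checks eligibility when "laboratory tests are resulted and the patient no longer meets one or more of the eligibility criteria, treatment must be held". The study calendar lists ECHO under X-rays and scans, not under laboratory studies.
- Calendar footnote 17 points only to 5.2. Footnote 9 waives a repeat ECHO at crossover when there was no significant change from baseline, which is again a change rule. Footnote 19 sets time windows for assessments.
- 8.4 suggests holding treatment at a 10% decrease, leaves the action to the physician, and gives no absolute value.
- The Study Chair clause applies if a question arises. A fall that satisfies 5.2f need not raise one.

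None of these states a floor.

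**2. Lowest EF that 5.2f alone admits, for baseline B**

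- Points: B − 10. This is below 45 when B < 55. At B = 45 it is 45 − 10 = 35%.
- Relative: 0.9 × B. This is below 45 when B < 50. At B = 45 it is 0.9 × 45 = 40.5%.
- At higher baselines 5.2f is at least as strict as 5.1m.

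**3. Number who could reach Step 2**

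Inputs from 11.2: 63 Arm 1 patients, median PFS 9 months, exponential. One cycle is 28/30.44 = 0.92 months, and 12 cycles are 11.04 months.

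- Progression after Cycle 1 and within 12 cycles: exp(−ln2 × 0.92/9) − exp(−ln2 × 11.04/9) = 0.932 − 0.427 = 0.504, and 63 × 0.504 = 31.8.
- Under 7.1b a patient who progresses in Cycle 1 continues treatment and may qualify later. Counting these, 63 × (1 − 0.427) = 36.1.

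Deaths, removals for toxicity and the other items of 5.2 lower both figures.

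**4. Number admitted below 45% (assumption)**

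The documents give no EF distribution. I assumed normal baseline EF with mean 55, 60 or 63 and SD 5, 6 or 8, cut to 45–80. Change was normal with mean/SD 0/5, −2/6 or −4/8. That makes 27 settings, each simulated and multiplied by 31.8, before any filter other than 5.2f.

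| Baseline mean | Points reading | Relative reading |
|---|---|---|
| 55 | 1.6–2.8 | 0.4–0.7 |
| 60 | 0.3–1.3 | 0.05–0.3 |
| 63 | 0.1–0.7 | 0.01–0.15 |
| Median of 27 settings | 0.8 | 0.15 |

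With a pool of 36.1 the top figure becomes 2.81 × 36.1/31.8 = 3.2.

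**5. The 5.1k items**

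Heart failure of NYHA Class III or IV with an EF fall is covered by 5.2f. A current Grade 3 arrhythmia counted as a toxicity is covered by 5.2c. Unstable angina and infarction within 6 months are not named.

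The infarction gap is narrow:

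- Under 8.3a a related event of Grade 3 or higher means a hold, and a dose reduction if it has not resolved by the next scheduled dose (gaps of 1, 6, 1, 6, 1 and 13 days).
- 8.2d forbids re-escalation, 5.2d then bars crossover, and 7.6f removes patients with delays over 4 weeks.
- What remains is mainly an infarction judged unrelated, resolved before the next dose, or below Grade 3.

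The table in Section 2.0 gives ischemic heart disease of Grade 3 or higher in 7/526 = 1.3% (exact 95% CI 0.5–2.7%). Times 31.8, that is about 0.4 patients (0.2–0.9) before any filter.

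**The case against.** **A change-from-baseline rule is reasonable here, and crossover is screened more closely than Arm 2.** Step 2 patients have already received 27 mg/m². Arm 2 patients go to 56 mg/m² in Cycle 2 with a pre-study ECHO and no further scheduled one until after Cycle 3, whereas crossover needs an ECHO within 28 days. This stands as context and is why the point is minor. It does not remove the inconsistency. Every eligible Arm 2 patient had EF of at least 45% on the entry ECHO, while 5.2f can pass a patient whose current ECHO is known to be below it.

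**5.2f does not act alone.** This stands. A reader might infer that a patient with EF of 35% may enter Arm 3. The documents do not establish that: decreased ejection fraction is a listed carfilzomib toxicity (3.1c), and 5.2c requires recovery to Grade 2 or lower. The grading cut-offs are not in the documents, so the 35% and 40.5% minima belong to 5.2f only.

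**The documents do not show more heart failure at the higher dose.** This also stands. A reader might infer that 56 mg/m² is shown to be more dangerous at low EF. Section 2.0 reports cardiac failure of Grade 3 or higher in 30/526 (6%) across studies at up to 27 mg/m², and in 6% of 65 patients at 20/56 mg/m². The comparison is across studies and small, but it is the only one given.

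**Re-imposing all of 5.1k would cost more than it gains.** This stands. It would bring back active infection and an open-ended exclusion for clinically significant illness. Pneumonia is listed at 4–20% in 3.1c, so the crossovers lost could outnumber those the EF floor affects.

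**Conclusion.** The gap is real but small. Section 5.2f has no EF floor, no other text supplies one, and on 5.2f alone patients with baseline EF of 45 to below 55% (points) or 45 to below 50% (relative) can be registered below the Step 1 limit. The expected number is about 0.1 to 2.8 of 32 (points, median 0.8) or 0.01 to 0.7 (relative, median 0.15), and up to about 3.2 if the pool is 36. These counts depend entirely on the assumed EF distributions and precede the other filters, of which 5.2c may be the most important.

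The conclusion goes no further. It does not show excess cardiac risk at 56 mg/m², a wide opening for recent infarction, or any effect on the primary analysis. Step 1 accrual is permanently closed, so an amendment matters only for Arm 1 patients still able to cross over. This is a cheap improvement.

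**What to change.** Add to 5.2f that the patient must have EF of at least 45% on the ECHO obtained within 28 days before Step 2 registration. Add to 5.2 only the two cardiac items of 5.1k that it does not cover: no unstable angina, and no myocardial infarction within 6 months. Do not re-impose the rest of 5.1k. With the floor in place, the lowest EF at crossover is 45% for every baseline, on either reading of 10%.

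Leave the 10% limit and the Study Chair clause as they are. Whether 10% means points or relative is a separate question for the sponsor. If sites now read it as relative, changing it to points would newly admit about 2.2 to 5.1 of 32 patients under the same assumptions, even with the floor.

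**Cost.** A short amendment and no new test, since 5.2f already requires the ECHO. On the order of one patient, possibly up to about three, would lose crossover and leave the Arm 3 response estimate (objective 1.2b), including a patient with a small fall such as 46% to 44%. If the sponsor intends a lower floor for patients who have already tolerated 27 mg/m², that value should be stated instead.
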